Single-Arm, Single-Center, Randomized, Single-Masked Study to Evaluate Restylane-Defyne for Canalicular Occlusion in Participants with Mild to Moderate Dry Eye Disease

Protocol Number: 0918

Protocol Date: July 9, 2018

Version 1.0

Revision History None

Principal Investigator
and Sponsor [name]
The Eye Care Institute
[name]
[name]

Monitor [name]
[name] Consulting, Inc.
[name]
[name]

PROTOCOL 0918 STUDY SYNOPSIS

Protocol Title	Single-Arm, Single-Center, Randomized, Single-Masked Study to Evaluate Restylane-Defyne for Punctal Occlusion in Participants with Mild to Moderate Dry Eye Disease
Study Period	Up to 3 months
Study Population	13 adult participants with mild to moderate dry eye disease
Primary Study Objectives	Safety and effectiveness assessments of Restylane-Defyne for punctal occlusion
Treatments	Participants will receive Restylane-Defyne in the inferior punctum of one eye and a sham injection in the inferior punctum of the fellow eye.
Study Design	Prospective, randomized, single-masked study with unilateral placement of Restylane-Defyne.
Sample Size	Up to 13 participants, with a goal of 10 participants finishing study.
Examination Schedule	Participants will have a Baseline Visit within 30 days prior to the initial device application. Device application will be initiated at Day 0 with follow-up visits at 3 days, 14 days and 42 days. Participants will exit the study after the 6-week visit exam.

Clinical Assessments

Assessments performed will include:

- Ocular Surface Disease Index questionnaire
- Slit-lamp biomicroscopy with grading of corneal staining
- Schirmer test with topical anesthetic
- Tear break-up time
- Tear meniscus height
- Corrected Distance Visual Acuity

Study Endpoints

- **Primary effectiveness endpoint**

Change in Schirmer score from baseline

- **Additional effectiveness endpoints**

Changes in OSDI score, corneal staining score, tear break-up time and tear meniscus height

- **Primary safety endpoint**

Proportion of participants that experience one or more device-related adverse events (e.g., irritation, conjunctival injection, epiphora, subconjunctival hemorrhage, canaliculitis, punctal stenosis, eyelid telangiectasia, eyelid edema, eyelid induration, eyelid erythema).

- **Additional safety assessments**

Corrected distance visual acuity, slit lamp biomicroscopy findings

Inclusion Criteria

To be eligible for the study, potential participants must meet all of the following inclusion criteria at the Screening Visit:

- Twenty-one (21) to 80 years of age
- Baseline Ocular Surface Disease Index score of at least 13 with no more than 3 responses of “not applicable” for each eye individually
- In the study eye, a baseline Schirmer test with anesthetic of ≤ 10 mm/5 minutes
- Literate, able to speak English and able to complete the questionnaire independently
- Willing to sign the informed consent and deemed capable of complying with the requirements of the study protocol.

Exclusion Criteria

- To be eligible for the study, potential participants must not meet any of the following exclusion criteria:
 - Use of ophthalmic cyclosporine or lifitegrast within 30 days prior to Day 0
 - History of surgical punctal occlusion (e.g., cauterity), canalicular infection or canalicular surgery
 - Corneal transplant in either eye
 - Ocular surgery (such as cataract surgery or LASIK) in either eye within six months of the Baseline Visit
 - A systemic condition or disease not stabilized or judged by the investigator to be incompatible with participation in the study (e.g. current systemic infection, uncontrolled autoimmune disease, uncontrolled immunodeficiency disease)
 - The history or presence of any ocular disorder or condition in either eye that, in the opinion of the investigator, would interfere with the interpretation of the study results (e.g., significant corneal or conjunctival scarring, pterygium or nodular pinguecula; current ocular infection (except mild blepharitis), conjunctivitis or inflammation not associated with dry eye; anterior (epithelial) basement membrane corneal dystrophy or other clinically significant corneal dystrophy or degeneration; history of ocular herpetic infection; evidence of keratoconus; lid or lacrimal cancer.

- Active severe systemic allergy, seasonal allergies, rhinitis or sinusitis requiring treatment (i.e. antihistamines, decongestants, oral or aerosol steroids)
- Use of steroids, including administration by systemic, inhaled or topical ocular routes (dermatologic steroids not applied to the eyelids are allowed)
- Participation in a clinical trial during the past 30 days
- Women who are pregnant, planning a pregnancy, or nursing at study entry.

TABLE OF ABBREVIATIONS

AE	Adverse event
ATD	Aqueous tear deficiency
CDVA	Corrected distance visual acuity
CE	Conformité Européenne (European Conformity)
CRF	Case report form
DED	Dry eye disease
ETDRS	Early Treatment of Diabetic Retinopathy Study
FDA	United States Food and Drug Administration
GCP	Good Clinical Practice
HA	Hyaluronic Acid
ICH	International Conference on Harmonisation
IRB	Institutional Review Board
ISO	International Standards Organization
logMAR	Logarithm of the minimum angle of resolution
NEI	National Eye Institute
OSDI	Ocular Surface Disease Index
PP	Per protocol
SAE	Serious adverse event
UADE	Unanticipated adverse device effect

1. INTRODUCTION

1.1. Background

The 1995 National Eye Institute (NEI)/Industry Dry Eye Workshop defined dry eye disease (DED) as a multifactorial disease of the tears and ocular surface that results in symptoms of discomfort, visual disturbance, and tear instability with potential damage to the ocular surface. Dry eye disease has a complex pathophysiology and a multifactorial etiology related to an inadequacy of one or more layers of the tear film. It is accompanied by increased osmolarity of the tears and inflammation of the ocular surface.¹ An estimated 25 million Americans are reported to have DED,² one of the most common reasons patients seek care with their eye care professional.³

DED has multiple causes and consequences, ranging in severity from mild discomfort and pain to a decrement in visual acuity resulting from irregularities in the corneal surface. Signs of DED include reduced tear volume, delayed tear clearance, abnormal tear osmolarity, decreased tear breakup time, punctate keratitis and distorted mires on keratometry or corneal topography. Symptoms include dryness, grittiness, burning, stinging, discomfort, photophobia, redness, tearing, reduced ability for prolonged reading or computer work, and fluctuating vision. These symptoms are typically worse later in the day and can be triggered or exacerbated by environmental conditions such as low humidity.

The severity and prevalence of DED in the general population increases with age and is particularly common in post-menopausal women and in those age 65 and older. While patients with mild to moderate dry eye experience a range of complaints, as described above, patients with severe dry eye are at risk for more serious ocular findings, such as punctate keratopathy evidenced by significant fluorescein staining of the cornea. More severely affected patients can experience a quality of life deficiency comparable to that of moderate to severe angina.⁴ Studies suggest that dry eye is associated with significant impact on visual function, including reading and driving⁵ as well as daily activities, social and physical functioning, workplace productivity and quality of life.⁶

Treatment for DED is generally palliative in nature and intended to supplement the patient's natural tears or to improve the residence time of the limited volume of tears present. Depending on the severity of disease and the underlying etiology of DED, options include artificial tear substitutes (solutions, ointments, and gels), punctal plugs, warm compresses, environmental modification, omega-3 fatty acid supplements, and moisture chamber goggles.^{7, 8} For patients with an inflammatory component to their DED, topical cyclosporine (Restasis; Allergan) and lifitegrast (Xiidra; Shire) are options, and an eyelid thermal pulsation system (Lipiflow Thermal Pulsation System; TearScience Inc.) can be used by patients with concomitant evaporative dry eye (i.e. lipid deficiency dry eye). Patients with aqueous tear deficiency can use a nasal neurostimulator to temporarily increase tear production (TrueTear; Allergan). Patients with more severe disease may be treated with punctal cauterity, systemic cholinergic agonists, systemic anti-inflammatory agents, mucolytic agents, autologous serum tears, PROSE scleral contact lenses⁹ and tarsorrhaphy.

The most commonly used palliative option for DED, artificial tear substitutes, have significant limitations as therapeutic modalities for this condition. Many artificial tear formulations contain preservatives such as benzalkonium chloride, which have been shown to be toxic to the corneal epithelium. Although commercially available, preservative-free artificial tear products include a risk of microbial contamination if improperly stored, a limited time after opening before disposal, and a significantly greater expense than the preserved option.

Punctal plugs are associated with poor retention and complications. A study focused on the time course of retention showed that 29% of plugs were lost within the first month of use¹⁰ and another showed that only 56% of silicone plugs were retained after two years.¹¹ Complications include plug migration, biofilm formation and infection.¹² Punctal plugs that are displaced into the lacrimal system may pass through the system, but blockage and secondary infection have been reported.

Given the limitations of the most commonly available therapies for DED (artificial tears and punctal plugs), it is not surprising that DED continues to be considered one of the most poorly treated diseases in ophthalmology.

1.2. Cross-Linked Hyaluronic Acid as a Device for Punctal Occlusion

Hyaluronic acid (HA) is a colorless and odorless mucopolysaccharide gel that occurs naturally in the human body, including in the eye, and serves as a scaffolding for collagen.

Hyaluronic acid is a substance well known in medicine with several FDA approved applications. HA has been used for years by cataract surgeons, who inject it directly into the anterior chamber of the eye to maintain space during surgery. More recently HA has been utilized to fill wrinkles in the face. Approved for this indication (PMA P140029), Restylane Defyne is a sterile transparent gel composed of cross-linked sodium hyaluronate of bacterial origin. The product has a HA concentration of 20 mg/ml in phosphate buffered saline at pH 7 and contains 3 mg/ml lidocaine hydrochloride added to the gel to achieve a pain-relieving effect.

Adding HA to artificial tears has been reported to be beneficial in treatment of dry eyes.¹³ Because HA is soft enough to conform to the delicate inner walls of the canaliculus and block tear outflow, a canalicular plug made of HA could be useful in blocking the outflow of tears and also potentially adding its own lubricating effects. The HA would be injected into the canaliculus below the lid margin and would not rub on the lid or irritate the eye.

A unique advantage of the HA plug is full reversibility. HA is degraded by the enzyme hyaluronidase, and this is routinely used in eye surgery and with facial fillers. The effect of removing the HA is almost instantaneous. If a patient no longer needed plugs, then the procedure to remove an HA plug is to irrigate the tear duct with hyaluronidase. Both hyaluronic acid and hyaluronidase are FDA approved compounds in eye and skin procedures, with a long safety record. The placement of these products does not require

injection with a needle, but rather a gentle, simple placement with a tapered cannula in an existing body cavity of the tear duct outflow system, the canaliculus.

1.3. Summary of Findings from Previous Studies

In a pilot clinical study, Restylane was used to bilaterally occlude the lower lacrimal canaliculi in 74 participants. A total of 148 plugs were inserted as all participants had both lower puncta treated. 58 patients completed the study; 46 patients were female and 12 were male. Of the patients that did not complete the study, most missed a critical follow up visit and were excluded from evaluation per the study protocol. No patient dropped out due to dissatisfaction or a complication. The average age in the study was

66.5 years. All but 3 participants were Caucasian (2 African Americans and 1 Asian). The investigator noted that the HA plug was easy to insert.

A statistically significant increase in Schirmer score was observed in each eye at the 1- and 3-month visits by two-tail t-test (Figure 1).

[figure not shown]

Figure 1. Schirmer scores. **p = 0.0006 and 0.0015 at 1 and 3 months, respectively; *p = 0.028 and 0.032 at 1 and 3 months, respectively.

In addition, significant improvements in tear break-up time (TBUT) and tear meniscus height were observed (Figures 2 and 3).

[figure not shown]

Figure 2. TBUT. ***p < 0.000 at 1 and 3 months.

[figure not shown]

Figure 3. Tear meniscus height. ***p < 0.000 at 1 and 3 months.

When questioned at 6-months, 83% of participants responded that they would have the treatment again. On a numerical scale, with “1” for agree to “5” for disagree, the average score was 2.4 when patients were asked if their eyes felt better after receiving the HA plug. Of note, these numerical values were reported at a 6- month phone interview, indicating that some patients were benefitting from the HA filler even after 6 months from injection.

There was one case of conjunctivitis that resolved and was believed to be an incidental viral infection. There were no other adverse events reported, including no canaliculitis, swelling, bruising or intraocular inflammation.

A complete study report is provided in Appendix D, Pilot Study Report.

1.4. Risks and Benefits.

The risks associated with the use of this non-significant risk device are low. Restylane-Defyne is an approved product, and HA has been used as both a topical and intracameral ocular agent. Punctal plugs in general are not considered significant risk devices, and the use of cross-linked HA for punctal occlusion has previously been recognized as a non-significant risk device by the Sarasota Memorial Hospital Institutional Review Board in Sarasota, FL. For further information see documentation provided in Appendix C, Correspondence with Sarasota Memorial Hospital Institutional Review Board.

Potential adverse events which may occur during the course of this study include irritation, conjunctival injection, epiphora, subconjunctival hemorrhage, canaliculitis, punctal stenosis, eyelid telangiectasia, eyelid edema, eyelid induration and eyelid erythema. Potential benefits include decreased signs and symptoms of dry eye disease.

2. STUDY OBJECTIVES

The objective of this pilot study is to investigate the safety and effectiveness of HA lacrimal occlusion in patients with mild to moderate dry eye disease.

3. STUDY DESIGN

3.1. Description of Study Design

The study is a single-arm, single-center, randomized, single-masked prospective study to evaluate Restylane-Defyne for canalicular occlusion in participants with mild to moderate dry eye disease.

Each participant will have a Screening Visit to determine eligibility. Prior to performing any testing specifically for the Screening Visit, participants will be provided with an IRB approved informed consent form and be given the chance to review and ask questions before written informed consent is obtained. The Screening Visit should occur within 30 days prior to application of the HA gel on Study Day 0 and may occur on Day 0. Participants that meet all eligibility criteria will be invited to participate in the study.

Participants that return or are present for Study Day 0 will be enrolled in the study and will receive the device. Participants will be followed for 42 days and will be seen for follow-up exams at 3, 14 and 42 days.

Participants may continue to use their artificial tears. The use of artificial tears will be recorded.

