3.6. Randomization

This is a single-arm, randomized, single-masked study in which one eye will receive the device in the lower canaliculus and the fellow eye will receive a sham injection of saline in the lower canaliculus. The eye which receives the device will be determined by a randomization sequence. The participant will remain masked as to which eye received the device and which eye received the sham.

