3.9. Concomitant Medications and Therapies

All concomitant medications used within the 30 days prior to the screening visit, including medications used for relief of dry eye symptoms, will be documented on the case report form. Any initiation of new medications or changes to current medications during the course of the study should be recorded on the appropriate case report form. No other experimental drug or device should be used within 30 days prior to the Screening Visit or during the course of the clinical trial.

At the end of the Screening Visit, participants should be instructed not to use perfume or make-up on study days. Participants should also be instructed to refrain from administration of any chronic ophthalmic medication for two hours before their visit.

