4.6. Effectiveness Analyses

The assessment of effectiveness will be based on the changes in the primary and secondary effectiveness endpoints from baseline to 6 weeks in the eye which receives the device as compared with the eye which receives the sham injection.

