7.4. Records

7.4.1. Source Documents

Source documentation for this study will be maintained to document the application and study course of each participant and to substantiate the integrity of the trial data. Source documentation will include, but may not be limited to, worksheets, hospital and/or clinic or office records documenting participant visits including study and other treatments or procedures, medical/ophthalmologic history and physical examination information, laboratory and special assessment results, pharmacy records, device accountability records, and medical consultations. In this study, case report forms can be used as source documents where appropriate.

The investigator is responsible for maintaining adequate case histories in the source documents of each participant. The following data will be reported by the investigator in the source medical records of each participant enrolled in the study:

- The date the participant entered the study and the participant number
- The study protocol number
- The date that informed consent was obtained
- Evidence that the participant met the study eligibility requirements (e.g., medical history, study procedures and/or evaluations)
- The dates of all study-related participant visits
- Evidence that required procedures and/or evaluations were completed
- Use of any concurrent medications
- Occurrence and status of any adverse events
- The date the participant exited the study and a notation as to whether the participant completed the study or was discontinued, including the reason for discontinuation.

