9.2. Appendix B – Examinations and Procedures

9.2.1. Questionnaire

To minimize bias, participants will be asked to complete the questionnaire independently and in private after instructions have been provided by site personnel. The questionnaire should be completed twice and answered by the participant with reference to each eye individually.

Ocular Surface Disease Index (OSDI)

The OSDI is a 12-item questionnaire generated by the Outcomes Research Group at Allergan (Irvine, CA),¹⁴ which asks participants to describe the severity and the nature of their irritation symptoms. The participant will answer the 12 questions by circling the number that best represents each answer: 4 (all of the time), 3 (most of the time), 2 (half of the time), 1 (some of the time), or 0 (none of the time). The final score for the questionnaire is calculated as follows:

Add subtotals from Sections I, II, and III = A

Determine total number of questions answered from Sections I, II, and III (do not include N/A) = B

Final OSDI score = A x 25 divided by B

An example of the questionnaire is as follows:

Ocular Surface Disease Index® (OSDI®)²

Ask your patients the following 12 questions, and circle the number in the box that best represents each answer. Then, fill in boxes A, B, C, D, and E according to the instructions beside each.

Have you experienced any of the following during the last week?	All of the time	Most of the time	Half of the time	Some of the time	None of the time
1. Eyes that are sensitive to light? ...	4	3	2	1	0
2. Eyes that feel gritty?	4	3	2	1	0
3. Painful or sore eyes?	4	3	2	1	0
4. Blurred vision?	4	3	2	1	0
5. Poor vision?	4	3	2	1	0

Subtotal score for answers 1 to 5

(A)

Have problems with your eyes limited you in performing any of the following during the last week?	All of the time	Most of the time	Half of the time	Some of the time	None of the time	N/A
6. Reading?.....	4	3	2	1	0	N/A
7. Driving at night?	4	3	2	1	0	N/A
8. Working with a computer or bank machine (ATM)?.....	4	3	2	1	0	N/A
9. Watching TV?	4	3	2	1	0	N/A

Subtotal score for answers 6 to 9

(B)

Have your eyes felt uncomfortable in any of the following situations during the last week?	All of the time	Most of the time	Half of the time	Some of the time	None of the time	N/A
10. Windy conditions?.....	4	3	2	1	0	N/A
11. Places or areas with low humidity (very dry)?	4	3	2	1	0	N/A
12. Areas that are air conditioned?...	4	3	2	1	0	N/A

Subtotal score for answers 10 to 12

(C)

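### Effectiveness compares one eye with the other, but artificial tears may continue with no request for equal use in both eyes and no recording by eye

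*Protocol*

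**What the plan says.** **The contrast.** Protocol Section 4.6 bases effectiveness on changes from baseline to 6 weeks "in the eye which receives the device as compared with the eye which receives the sham injection". Each participant supplies both eyes.

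**Artificial tears.** Section 3.1: "Participants may continue to use their artificial tears. The use of artificial tears will be recorded". Section 3.9 adds that concomitant medications from the 30 days before screening, "including medications used for relief of dry eye symptoms, will be documented on the case report form", and that "Any initiation of new medications or changes to current medications during the course of the study should be recorded". Section 7.4.1 lists "Use of any concurrent medications" among the items for the source records. None of these mentions the eye treated, and none asks for equal use in both eyes.

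**Pre-visit hold.** Section 3.9: "Participants should also be instructed to refrain from administration of any chronic ophthalmic medication for two hours before their visit".

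**Per-eye symptoms.** Section 9.2.1 (Questionnaire): "The questionnaire should be completed twice and answered by the participant with reference to each eye individually". The items ask about the past week.

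**Masking.** Section 3.6: "The participant will remain masked as to which eye received the device and which eye received the sham".

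**The concern.** A fellow-eye design works because everything except the treatment is shared by the two eyes. Artificial tears are an exception, because a participant can put them in one eye and not the other. They are also the co-treatment most likely to change what the participant reports about that eye. Masking stops participants from dosing by knowledge of allocation, but not from dosing the eye that feels worse, and how each eye feels may depend on the device.

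If that happens, the OSDI contrast compares device plus some drops with sham plus some other amount of drops. A record kept per participant cannot show it. No later analysis plan can repair this, because the treated eye would never have been captured. At stake is the interpretation of one secondary endpoint, and possibly a second, in a study that aims for 10 completers.

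**Working it through.** The protocol gives no figure to reproduce: Section 4.1 reports no sample size calculation and Section 4.2 no hypothesis. The check is a comparison of sections, followed by a short illustration.

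**1. Where the protocol specifies the eye.**
- OSDI: by eye at every visit (Sections 3.7, 3.8 and 9.2.1; the Appendix A row specifies OD and OS separately).
- Device and sham: by eye, by randomization (Section 3.6).
- Artificial tears: recorded, eye not mentioned (Sections 3.1, 3.9 and 7.4.1). Appendix A has no row for tears or concomitant medication.

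The outcome and the treatment are therefore fixed by eye, but the main permitted co-treatment is not.

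**2. Which endpoints are exposed.**
- *OSDI:* exposed. With a one-week recall, a two-hour hold cannot protect it.
- *Corneal staining:* possibly exposed. A two-hour hold may do little for it.
- *Tear break-up time and tear meniscus height:* same-day measures, exposed mainly if tears fall outside the hold. The hold covers chronic ophthalmic medication. Regularly used tears may fit that wording, but as-needed tears are not clearly covered.
- *Schirmer (primary):* little affected. It is done under anesthetic, after excess moisture in the inferior fornix has been removed (Section 9.2.5).

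**3. Direction.** Let C = (OSDI change in the device eye) − (OSDI change in the sham eye). Lower OSDI is better, so a device benefit makes C negative. Suppose extra drops lower the score of the eye that gets them by s points.
- Drops in the sham eye move C by +s, toward zero when the device helps. This is plausible if the sham eye feels drier.
- Drops in the device eye move C by −s, away from zero when the device helps. This is also possible: Sections 1.4 and 6.4 list irritation and conjunctival injection as anticipated events.

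Nothing in the protocol says which would prevail.

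**4. Size, as an illustration only.** Section 9.2.1 gives OSDI = A × 25 / B, where A is the item sum and B the number of items answered. One category on one item is worth:
- B = 12: 25/12 = 2.08 points
- B = 9 (three items not applicable, the most that Section 3.3.1 allows at entry): 25/9 = 2.78 points

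Let k items fall by one category in one eye only, in m of n completers, all in the same eye group. Then

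shift in mean C = (25/B) × k × m / n.

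The synopsis gives the goal of n = 10 completers. The ranges k = 1 to 3 and m = 1 to 5 are assumptions and are not in the protocol.

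| n | B | k = 1, m = 1 | k = 3, m = 5 |
|---|---|---|---|
| 10 | 12 | 2.083 × 1 × 1/10 = 0.21 | 2.083 × 3 × 5/10 = 3.13 |
| 10 | 9 | 2.778 × 1 × 1/10 = 0.28 | 2.778 × 3 × 5/10 = 4.17 |
| 13 | 12 | 2.083 × 1 × 1/13 = 0.16 | 2.083 × 3 × 5/13 = 2.40 |
| 13 | 9 | 2.778 × 1 × 1/13 = 0.21 | 2.778 × 3 × 5/13 = 3.21 |

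The sign follows from step 3. If some participants favor the sham eye and others the device eye, the shifts partly cancel. The 15-fold spread in each row comes entirely from the assumed k and m (3 × 5 = 15). The table shows how the scale responds, not what is likely.

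**The case against.** The strongest case against is that this is silence on an operational detail and not an error. Letting symptomatic participants keep their usual tears is a defensible choice. Use is recorded, and starting extra drops in one eye is arguably a change that Section 3.9 already requires to be recorded. The case report form is not shown and may well have separate columns for each eye. Participants are masked, the primary endpoint is hardly touched, and the study is a pilot without a hypothesis.

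Most of this stands and limits the weight of the point. It does not remove it. The protocol specifies the eye where it wants it, as for OSDI, and does not do so for tears. A request to treat both eyes alike is a participant instruction, which belongs in the protocol and cannot be added at analysis.

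A reader might infer three stronger things that the protocol does not support:
- *That unequal use would understate the device and could not create a false benefit.* Dilution is plausible, but an irritated device eye could draw the extra drops, so the direction is open.
- *That equal dosing would leave no bias.* Section 1.2 describes the gel as blocking tear outflow, so the same drop may stay longer in the occluded eye.
- *That the point range above measures the bias.* It rests on chosen inputs. The entry score of 13 is no yardstick for it either, because it is an eligibility level and not a between-eye difference.

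**Conclusion.** The point holds as a cheap improvement. The between-eye contrast in Section 4.6 is open to unequal, symptom-driven use of artificial tears, and the protocol neither discourages such use nor requires the record that would reveal it. OSDI is exposed, corneal staining possibly so, and the primary Schirmer endpoint little.

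Neither the direction nor the size of the distortion can be derived from the protocol. The only figures it supports are the 2.08 or 2.78 OSDI points per category per item; anything beyond that depends on how many participants dose unequally and how much the drops help. The conclusion assumes that some participants would give drops by symptom in one eye, and that the unseen case report form does not already separate the eyes. It is not a claim that tear use goes unrecorded or that continuing tears should be forbidden.

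**What to change.** In Sections 3.1 and 3.9:

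1. Record the artificial tear product and drops per day separately for OD and OS at each visit.
2. Instruct participants to keep their usual product and regimen through Day 42 and, when they use tears, to treat both eyes alike. Record departures by eye and do not treat them as protocol violations.
3. As a minor addition, name artificial tears in the two-hour pre-visit hold. This helps only the same-day measures (tear break-up time and tear meniscus height), not OSDI.

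The first item matters most, since it makes any imbalance visible whatever its direction.

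**Cost.** Two extra case report form fields per visit (one per eye) and one participant instruction. Compliance is self-reported. Some drops will go into an eye that would otherwise have had none, and if that is the occluded eye they may be retained longer. Equal dosing therefore reduces differential use without guaranteeing zero bias, which is why the instruction should not be a strict rule.
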